| Complete blood count | X ^j | X | X | X | X | X | X | X | X | X | X | X | X | X | X | X |
| Blood sample for PT and PTT for INR | X | | | | | | | | | | | | | | | |
| Blood samples for lymphocyte subset analysis ^o | X ^j | X | X | X | X | X | X | X | X | X | X | X | X | X | X | X |
| Blood samples for PD and exploratory biomarkers ^p | X ^f | | | | | | | X | | | | X | X | X | X | X |
| Blood samples (isolation of PBMCs) | X ^f | X | X | X | X | X | X | X | X | X | X | X | X | X | X | X |
| Urine pregnancy test (females of CBP only) ^q | X | | X | X | X | X | X | X | X | X | X | X | X | X | | |
| Serum pregnancy test (females of childbearing potential only) | X | | | | | | | | | | | | | | | X |
| Blood sample (storage for immune status) ^f | X ^f | | X | | X | X | | X | | | | X | X | X | X | X |
| MMSE ^s | X ^f | | | | X | X | X | X | X | X | X | X | X | X | X | X |
| FAQ ^s | X ^f | | | | X | X | X | X | X | X | X | X | X | X | X | X |

| Phase | Open-label Extension Phase | | | | | | | | | | | | | | | UNS Visit ^e |
|--|----------------------------|-----------|----|----|----|-----|-----|-----|-----|-----|-----|-----|-----------------|------------------------|-----|------------------------|
| | Period | Treatment | | | | | | | | | | | | Follow-Up ^d | | |
| Visit ^a | 21 ^b | 22 | 23 | 24 | 25 | 26 | 27 | 28 | 29 | 30 | 31 | 32 | ED ^c | 33 | 34 | |
| Day in OLE | 1 | 15 | 29 | 57 | 85 | 183 | 274 | 365 | 456 | 547 | 638 | 729 | | 757 | 813 | |
| Week in OLE | 1 | 3 | 5 | 9 | 13 | 27 | 40 | 53 | 66 | 79 | 92 | 105 | | 109 | 117 | |
| Weeks elapsed since 1st dose in OLE | 0 | 2 | 4 | 8 | 12 | 26 | 39 | 52 | 65 | 78 | 91 | 104 | | 108 | 116 | |
| Nominal months elapsed since first dose in OLE | 0 | | 1 | 2 | 3 | 6 | 9 | 12 | 15 | 18 | 21 | 24 | | 25 | 27 | |
| Procedures/ Assessments | | | | | | | | | | | | | | | | |
| C-SSRS | X ^f | | | | | | | | | | | X | X | | | |
| Clinical assessment of suicidal thinking and behavior ^t | | X | X | X | X | X | X | X | X | X | X | X | | X | X | X |
| Safety MRI and vMRI ^u | X ^f | | | | | | | | | | | X | X | | | X |
| Adverse events | X ^m | X | X | X | X | X | X | X | X | X | X | X | X | X | X | X |
| Dispense study drug | X ^v | | X | X | X | X | X | X | X | X | X | | | | | |

Notes for [Table 14](#)

C-SSRS = Columbia Suicide Severity Rating Scale, ECG = electrocardiogram, ED = Early Discontinuation, FAQ = Functional Assessment Questionnaire (also known as the Functional Activities Questionnaire), MMSE = Mini Mental State Examination, MRI = magnetic resonance imaging, OLE = Open-label Extension, PBMC = peripheral blood mononuclear cell, PD = pharmacodynamics, UNS = unscheduled, vMRI = volumetric magnetic resonance imaging.

- a: A window of ± 3 days will be permitted for Visits 22 and 23. A window of ± 7 days will be permitted for Visits 24 and 25. A window of ± 10 days will be permitted for Visit 26 to 32 inclusive. A window of ± 3 days will be permitted for the Follow-Up Visits. If a permitted visit windows is used, every effort should be made to bring the subject back in line with the “weeks elapsed since 1st dose in OLE” at subsequent visits.
- b: Visit 21 may occur on the same day or within 4 weeks of Visit 20 date. The Medical Monitor must be contacted if Visit 21 is to occur more than 4 weeks after Visit 20. Informed consent must be obtained prior to performing Visit 21 assessments.
- c: Subjects who discontinue taking study drug prematurely for any reason will undergo an ED Visit within 7 days of their last dose of study drug. In addition, Follow-Up Visits will be scheduled 4 and 12 weeks after the last dose of study drug (Visits 33 and 34 respectively).
- d: All subjects, regardless of whether they complete all 24 months of treatment or discontinue study drug prematurely, will complete the 2 posttreatment Follow-Up Visits; (ie, Visits 33 and 34). If clinically indicated, more frequent safety assessments can be made as UNS assessments or visits during the posttreatment Follow-up Period.
- e: Unscheduled visits may be conducted at any time that additional assessments, including MRI scans, are clinically indicated in the judgment of the investigator. Note that not all assessments indicated under UNS Visits need be conducted – actual assessments needed will be determined by the investigator and will be based on the specific visit needs.
- f: Result from Visit 20 will also serve as Visit 21 result. If the specified assessment was not performed at V20, it must be performed at Visit 21.
- g: Dermatologic assessment by the investigator must be performed at Visit 21 in addition to the centralized skin assessment (using standardized photography) performed at Visit 20.
- h: Only if clinically significant abnormalities are found at Visit 33 and the investigator considers it necessary to repeat at Visit 34.
- i: Measurements of body temperature and sitting blood pressure and sitting heart rate will be obtained.
- j: Result from Visit 20 will also serve as Visit 21 result if Visit 21 occurs within 10 days from Visit 20. If Visit 21 occurs more than 10 days after Visit 20, the assessment must be repeated at Visit 21.
- k: Examples of neurological signs that may indicate new central nervous system pathology that may need further investigation include (but not limited to) visual disturbance, dysarthria, dysphasia, muscle strength, limb weakness, hyperflexia, paraparesis, micturition difficulty or urgency or incontinence, ataxia, neuropsychiatric or cognitive decline in excess of expectations based on the subject’s recent history. The Brief Smell Identification Test (Sensonics Inc.) will be administered at the same visits and serves as part of the neurologic examination.
- l: Please refer to Section 9.4.7 which describes prohibited and permitted medications in the study.
- m: Result from Visit 20 will also serve as Visit 21 result if Visit 21 occurs on the same day as Visit 20. If Visit 21 occurs more than 1 days after Visit 20, the assessment must be repeated at Visit 21.
- n: Single 12-lead standard ECGs will be recorded. If the QTcF is greater than 450 ms, perform 2 more 12-lead standard ECGs 1 minute apart and take the mean of the 3 QTcF values.
- o: Reports of the lymphocyte subset analyses will be sent to the Sponsor only. Lymphocyte subsets will include but are not limited to the following cell surface marker assessments: CD4 [T helper cells], CD8 [cytotoxic T cells], CD19 [B cells], CD16/CD56 [NK cells] and CD14 [macrophages] and absolute lymphocytes. Regulatory T cells will also be measured. Viability staining may also be employed.
- p: PD blood samples should be collected at fasting or at least 2 hours after the most recent meal and, as far as is feasible, samples should be taken at the same time of day. All PD blood samples should be collected predose.
- q: If dipstick urinalysis performed at site is abnormal, a urine sample will be sent to the central laboratory for full urinalysis.

-
- r: Blood samples will be collected and stored. These samples may be used for exploratory biomarker analyses, or in the event that the subject develops treatment-emergent adverse events that warrant further investigation (eg, treatment-emergent infection), these samples may be tested to determine whether the subject already had prior exposure to any suspected infective agents.
 - s: The subject components of these assessments are to be completed in the morning whenever possible, or consistently at the same time of day. Ideally, the subject component of these assessments should be completed before more invasive assessments or procedures (eg, physical examination, ECG, blood draws).
 - t: The clinical assessment of suicidality will require input from both the subject and the study partner
 - u: MRI imaging will be conducted on separate days from the scheduled visits. Safety MRIs will be acquired using a standardized procedure that will include gradient echo, long tau inversion recovery, and diffusion-weighted imaging sequence images in MRI will be read by an approved central reader. MRI imaging should be conducted within 7 days before Visits 21 (where applicable) and 32. In the event of an Unscheduled Visit, the investigator in consultation with the sponsor will determine whether or not a safety MRI should be conducted. If an ED Visit takes place, an MRI is to be conducted if not already performed during the preceding 90 days.
 - v: The subject will take the first dose of study drug at the study site and the subject will be encouraged to stay at the site for an appropriate period of time as determined by the PI or Safety Physician for postdose medical observation. Subjects with pending INR and serum pregnancy results may begin dosing at Visit 21 if they satisfy all other OLE entry criteria.

EXTENSION PHASE STATISTICAL METHODS

Primary Endpoint

- Safety endpoints: AE, vital sign, ECG, physical examination, clinical laboratory test, any relevant test of cognitive function to evaluate decline, and MRI parameter (microhemorrhage, vasogenic edema, and other clinically significant abnormalities).

Secondary Endpoint

Changes from Core Study and OLE baselines in

- MMSE and FAQ at each visit assessed in the OLE Phase
- Plasma amyloid measurements at 12 and 24 months of OLE treatment
- Total hippocampal volume, left and right hippocampal volume, whole brain volume, and total ventricular volume with up to 24 months of OLE treatment as measured by vMRI

OLE PHASE ANALYSIS SETS

- The **OLE Safety Analysis Set (OLE-SAS)** is the group of subjects who receive at least 1 dose of study drug during the OLE Phase.
- The **OLE Full Analysis Set (OLE-FAS)** is the group of subjects who receive at least 1 dose of study drug during the OLE Phase and have at least 1 postdose efficacy assessment during the OLE Phase.
- The **OLE PD Analysis Set** is the group of subjects who have at least 1 posttreatment PD measurement in the OLE Phase.

Safety Analyses

Safety analysis will be performed similarly to the Core Study. All safety analyses will be based on OLE Safety Analysis Set. The incidence of AEs (including changes from baseline in physical and neurological examinations, and dermatological assessments), out-of-normal-range laboratory safety test variables, abnormal ECG findings, out-of-range vital signs, suicidality (C-SSRS), and changes from baseline in laboratory safety test variables, ECGs, safety MRI, vital sign measurements, and cognitive decline assessment such as MMSE will be summarized by using descriptive statistics.

Efficacy Analyses

The following secondary efficacy endpoints will be summarized by descriptive statistics and/or graphs, using OLE-FAS:

- Changes from Core Study and OLE baselines in MMSE and FAQ scores
- Changes from Core Study and OLE baselines in total hippocampal volume, left and right hippocampal volume, whole brain volume, and total ventricular volume at up to 24 months as measured by vMRI

The relationship between efficacy endpoints and biomarker endpoints will be explored using correlation analysis.

Pharmacodynamic Analyses

The OLE PD Analysis Set will be used for the summaries and analyses of PD biomarkers. The percentage change in plasma amyloid measurements from Core Study and OLE baselines to 12 and 24 months of OLE treatment will be analyzed and presented graphically.

SAMPLE SIZE RATIONALE

Subjects who complete the Core Study will have the option to participate in the OLE Phase. There is no sample size calculation for the OLE Phase.

PROTOCOL SIGNATURE PAGE

(revised per Amendment 05)

Study Protocol Number: E2609-G000-202

Study Protocol Title: A Placebo-Controlled, Double-Blind, Parallel-Group, Randomized, Dose-Finding Study To Evaluate the Safety and Tolerability of E2609 in Subjects With Mild Cognitive Impairment due to Alzheimer's Disease (Prodromal Alzheimer's Disease) and Mild to Moderate Dementia Due to Alzheimer's Disease (revised per Amendments 01 and 05)

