- Systemic or ocular immunosuppressive or immunomodulatory drugs are not permitted for a period of 5 half-lives or 60 days (whichever is longer) before randomization. However, during the treatment period of the study, short term (not more than 14 days) use of steroids up to the equivalent of prednisolone 40 mg once daily is permitted after discussion with the Medical Monitor. Dosing with study drug should be suspended from the time steroid treatment is started. Complete blood count and lymphocyte subsets should be determined prior to starting steroid treatment and continue to be monitored weekly. Study drug may be resumed after discussion with the Medical Monitor when the following conditions are met: (1) treatment with steroids has been completed for at least 1 week; (2) absolute lymphocytes not <LLN; (revised per Amendments 07) (3) no lymphocyte subsets are below the discontinuation threshold (for Core Study only); (4) the investigator considers that the medical condition which required treatment with steroids has improved or resolved. Weekly testing of lymphocyte subset counts (for Core Study only) and CBC with differentials is required for 4 weeks following resumption of study drug administration. (revised per Amendment 04)
- (revised per Amendment 06)

Subjects who initiate treatment with an AChEI or memantine during the study, or who change their dose of AChEI or memantine while on study, will be allowed to continue in the study, but their clinical efficacy data will be censored from the time of drug initiation for any efficacy analyses. (revised per Amendment 05)

Subjects taking all other non-prohibited concomitant medications must meet the following requirements:

- Must be on stable dose for at least 4 weeks before randomization, except for medications that are administered as short courses of treatment or which are to be used intermittently as needed. Subjects who are on anticoagulants may have a variable dose but should have stable anticoagulation control for at least 4 weeks before randomization. They may be required to stop their anticoagulant medication prior to CSF collection and then restart this medication after the LP procedure, as per local guidelines. (revised per Amendment 04)
- Medications that are used as needed, rather than on a stable daily basis, and which are central nervous system (CNS) active and may affect cognitive function, are not permitted during a period of 72 hours before cognitive testing

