Appendix 6 Open-Label Extension Phase

(revised per Amendment 07)

PRIMARY OBJECTIVE

- To assess the long-term safety and tolerability of daily dosing with elenbecestat (E2609) 50 mg in mild cognitive impairment (MCI)/Prodromal subjects and in subjects with Mild to Moderate Dementia due to Alzheimer's Disease

SECONDARY OBJECTIVES

- To explore the long-term effects of elenbecestat (E2609) on clinical status by assessment of:
 - a. The Mini-Mental State Examination (MMSE)
 - b. The Functional Assessment Questionnaire (FAQ; also known as the Functional Activities Questionnaire)
- To explore the long-term effects of elenbecestat (E2609) on:
 - a. vMRI including total hippocampal volume, left and right hippocampal volume, whole brain volume, and total ventricular volume with up to 24 months of treatment in the OLE Phase.
 - b. Plasma amyloid at 12 and 24 months of treatment in the OLE Phase

ELIGIBILITY CRITERIA

Subjects who do not meet all of the inclusion criteria or who meet any of the exclusion criteria will not be eligible to receive study drug.

Inclusion:

1. Subjects who complete the 18-month treatment and the 12-week follow-up period (Visit 20) in the Core Study and whose Visit 20 falls within a 4-week window from the start of the Open-label Extension (OLE) Phase (Visit 21). Permission must be obtained from the Medical Monitor if Visit 21 is to occur more than 4 weeks from Visit 20.
2. Subjects must continue to have an identified caregiver or informant who is willing and able to provide follow-up information on the subject throughout the course of the OLE Phase.

Exclusion:

1. Subjects who discontinue study drug prematurely during the Core Study are not eligible to participate in the OLE Phase.

2. Subjects with any active infection within 4 weeks of Visit 21.
3. Subjects with absolute lymphocyte count below the Lower Limit of Normal (LLN) within 10 days of Visit 21.
4. Subjects who develop the following conditions from the time of screening for the Core Study to the start of the OLE Phase:
 - a. Hepatic impairment, with total bilirubin greater than $1.5 \times$ upper limit of normal (ULN) or International Normalized Ratio (INR) greater than 1.7. Subjects with Gilbert's syndrome need not be excluded on the basis of an elevated bilirubin, provided that they have no other signs or symptoms suggestive of hepatic impairment.

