The primary reason for discontinuation and all other reason(s) contributing to the subject's discontinuation from study drug should be collected on the ED from study drug electronic case report form (eCRF) page (see Protocol [Section 9.5.5](#)). In addition, the date of last dose of study drug will be recorded on the Study Drug Dosing eCRF page.

Safety-related criteria for discontinuation of study drug include the following:

1. Absolute lymphocyte count will be monitored during the study. Should a subject develop lymphocytopenia (less than $800/\text{mm}^3$ or LLN, whichever is higher), a confirmation test should occur as soon as possible but no later than within 5 days with a repeat test of absolute lymphocytes. If confirmed, study drug administration should be interrupted for a minimum period of 2 weeks. Restart of study drug may take place only when absolute lymphocyte count returns to greater than LLN. Absolute lymphocyte count will be measured 4 weeks after restart of study drug. Subsequent measurements of absolute lymphocyte counts will follow the schedule of assessments and any results showing a Grade 2 or greater lymphocytopenia (less than $800/\text{mm}^3$) should be handled as above. If a 2nd occurrence of Grade 2 or greater lymphocytopenia (less than $800/\text{mm}^3$), that is confirmed on repeat testing, occurs within 6 months, then the subject should be discontinued permanently from the study drug.
2. A subject with any skin rash of moderate to severe intensity, or any rash lasting more than 72 hours regardless of severity (with the exception of oral or genital herpes as described in the next paragraph), will be discontinued from study drug and a dermatologic consult will be requested regardless of whether the rash is considered drug-related or due to other causes. For cases where the investigator suspects a drug rash, regardless of severity, the subject will be discontinued from study drug, a dermatologic consult will be requested, and a skin biopsy will be performed to confirm the diagnosis. The skin rash will be treated as per standard care and will be followed up until resolution regardless of etiology or severity.
3. Subjects who develop moderate to severe oral or genital herpes should be discontinued from study drug. Subjects who develop a mild case of oral or genital herpes may remain on study drug even if the event lasts more than 72 hours.

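### OLE restart after lymphocytopenia is tested against LLN alone, so if LLN is below 800/mm3 dosing may resume at a count that still meets the stop rule; the Grade 2 label also differs between Appendices 1 and 6

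*Protocol*

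**What the plan says.** **Interruption.** Appendix 6, Removal of Subjects from Therapy or Assessment, criterion 1, acts on a count less than 800/mm3 "or LLN, whichever is higher), a confirmation test should occur as soon as possible". If the repeat test confirms the result, drug is stopped for at least 2 weeks.

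**Restart.** The same criterion continues: "Restart of study drug may take place only when absolute lymphocyte count returns to greater than LLN". It then adds: "Absolute lymphocyte count will be measured 4 weeks after restart of study drug". Any later count below 800/mm3 goes through the same steps again. The sentence that opens "If a 2nd occurrence of Grade 2 or greater lymphocytopenia" makes a second confirmed count below 800/mm3 within 6 months a reason to stop drug for good.

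**Entry.** OLE exclusion 3 removes "Subjects with absolute lymphocyte count below the Lower Limit of Normal (LLN) within 10 days of Visit 21". It contains no 800 floor.

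**Grading.** Appendix 6 twice prints less than 800/mm3 beside the Grade 2 label. Appendix 1 has no Grade 1 for lymphocytes and begins Grade 2 below 700/mm3. Section 9.7.1.8.3 uses the Appendix 1 grades to define treatment-emergent markedly abnormal values (TEMAVs).

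The protocol gives neither the LLN for absolute lymphocytes nor the resolution to which counts are reported.

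**The concern.** A stop rule and its restart rule should not both be satisfied by the same value. Here the stop limit is the larger of two numbers and the restart limit is only one of them. Where 800 is the operative limit, recovery above it is not required before redosing.

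Lymphocyte reduction is a leading safety concern for this drug, safety is the OLE primary endpoint, and in the OLE the absolute count replaces the CD4, CD8 and CD19 thresholds used in the Core Study. The gap has two effects. Drug may be resumed below the limit that stopped it. The subject then faces a recheck against 800 that an unchanged count will fail, and a second confirmed failure within 6 months ends treatment.

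The grade conflict concerns reporting: the same count would be called Grade 2 when dosing is decided and would not be a TEMAV in the safety tables.

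**Working it through.** **Inputs** (counts per mm3)

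- Interrupt: confirmed count < max(800, LLN) (Appendix 6, criterion 1).
- Restart allowed: count > LLN (same criterion).
- Entry allowed: count ≥ LLN (OLE exclusion 3).
- Appendix 6 Grade 2 or greater: count < 800. Appendix 1 Grade 2 or greater: count < 700.
- LLN and reporting resolution: not stated, so assumed below.

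**Overlap of restart and interruption.** Both hold when LLN < count < max(800, LLN). If LLN ≥ 800, the upper limit equals LLN and the set is empty. If LLN < 800, the set is LLN < count < 800. For entry, replace the first < by ≤.

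Counts reported to 1/mm3:

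| Assumed LLN | Entry overlap | Restart overlap |
|---|---|---|
| 700 | 700–799 (100 values) | 701–799 (99) |
| 750 | 750–799 (50) | 751–799 (49) |
| 800, 850 or 1000 | none | none |

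Resolution matters. In steps of 0.01×10^9/L with LLN 0.70, the entry overlap is 0.70–0.79 and the restart overlap 0.71–0.79. In steps of 0.1×10^9/L with LLN 0.7, entry overlaps at 0.7 only. Restart does not overlap at all, because the first value above 0.7 is 0.8, which is not below 0.8.

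**One path through the rule, LLN assumed 700.** A subject is stopped at a confirmed 690. After 2 weeks the count is 750, which exceeds LLN, so restart is permitted. Four weeks later it is still 750, which is below 800, so the steps apply again. If the repeat test, due within 5 days, confirms it, this can be read as a second occurrence. Elapsed time is 2 weeks + 4 weeks + up to 5 days, well inside 6 months, and the subject could be stopped permanently with no fall since restart. A subject stopped at a confirmed 750 already met the restart condition on the day of stopping; only the 2-week minimum holds the drug back.

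**Comparison with the Core Study.** Section 9.3.3, criterion a, suspends below CD4 250, CD8 150 or CD19 50 cells/µL and resumes only above 396, 157 and 74. Each restart limit exceeds its stop limit, so no overlap is possible.

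**Grade check** (any LLN)

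| Count | Appendix 1 | Appendix 6 |
|---|---|---|
| 650, 699 | Grade 2 | Grade 2 or greater |
| 700, 750, 799 | ungraded | Grade 2 or greater |
| 800 | ungraded | ungraded |

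The conflict covers 700–799.

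**Reach.** At most 60 × 1.2 = 72 subjects are randomized, and only those who complete the Core Study can enter the OLE. The Appendix 5 combined mean CD4, CD8 and CD19 counts sum to 828.46 + 362.20 + 192.57 = 1383.23/mm3 before natural killer cells, so a total below 800 is well under typical.

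**The case against.** The strongest reply is that the overlap is conditional. If the central laboratory's LLN is 800/mm3 or more it is empty, and taking the higher of two limits may be no more than protective drafting. That stands. A reader might infer from Appendix 1, which has no Grade 1 and starts Grade 2 below 700 after alignment with the central laboratory's grading (revision history, Amendment 01), that the LLN is about 700. The inference is reasonable, but the protocol does not state it. At 0.1×10^9/L resolution, an LLN of 0.7 would leave no restart overlap.

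Second, the rule protects itself in part. LLN is a necessary condition for restart, not an instruction to redose. The 4-week recheck is read against 800, the investigator may stop drug at any time, and withholding drug for a laboratory result is recorded as an adverse event. A reader might infer that subjects would be kept on drug at low counts unnoticed; these provisions rule that out. They limit the consequence but leave the contradiction, and the recheck against 800 is what exposes a subject with an unchanged count to permanent discontinuation.

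Third, entry is a weaker case. The entry count follows about 12 weeks off Core Study drug, exclusion 11 covers clinically significant laboratory findings that the investigator judges relevant to safety or assessments, and blood counts are repeated at OLE weeks 2, 4, 8 and 12. A stricter limit on treatment than at entry can be defended.

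Fourth, a reader might extend the point to the post-steroid rule in Section 9.4.7, whose lymphocyte condition is "2) absolute lymphocytes not <LLN". That rule covers suspension for steroid use, not for lymphocytopenia. It also requires "1) treatment with steroids has been completed for at least 1 week", Medical Monitor discussion and improvement of the condition. Afterwards weekly "CBC with differentials is required for 4 weeks following resumption of study drug administration", and in the OLE those counts feed the 800 rule. It is not a separate defect.

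**Conclusion.** The wording mismatch is real and is fixed by the protocol itself: the stop limit carries an 800 floor that the restart limit lacks. If LLN is below 800 and the reporting resolution leaves a value strictly between LLN and 800, a subject may restart while still meeting the stop rule, then be re-interrupted or permanently discontinued without a new fall. The missing floor at entry is a lesser form of the same gap.

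The Grade 2 conflict at 700–799/mm3 does not depend on LLN. It is a labelling conflict only: Appendix 6 prints the number beside the label, so the dosing action is clear. It does not show that TEMAVs would be miscounted against their own definition.

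Severity is minor. Confidence is high for the mismatch and the grade conflict, and moderate that the overlap occurs in practice, since LLN and resolution are assumptions. The number of subjects affected cannot be derived.

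**What to change.** 1. In Appendix 6 criterion 1, allow restart only when the count is greater than LLN **and** at least 800/mm3. Both conditions should be written out. A shorthand of at least the higher of the two would permit restart at exactly LLN when LLN is 800 or more, which the current text forbids.
2. Preferably, apply a floor to OLE exclusion 3 as well: at least 800/mm3 and not below LLN.
3. Either use one Grade 2 lymphocyte cut-off in Appendices 1 and 6, or drop the grade label in Appendix 6 and keep the number.

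With changes 1 and 2, every permitted count is at least max(800, LLN), so the overlap is empty for any LLN and any resolution.

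The cost is a short protocol clarification with no added visits or samples. Any subject whose count lies between LLN and 800 would stay off drug longer or would not enter the OLE.
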